5.3 ANALYSIS OF CLINICAL PARAMETERS

Means, standard deviations, and ranges (min/max) will be derived from the continuous measurements. Frequencies, rates (cumulative incidence), and proportions will be used for summarizing the categorical and ordinal outcomes.

6.0 ADVERSE EVENT REPORTING

An Adverse Event (AE) is any untoward sign, symptom or disease observed during the study regardless of the suspected cause. Conditions or diseases that are pre-existing or chronic but stable are not Adverse Events. Changes in pre-existing or chronic conditions or diseases that are consistent with natural disease progression are not Adverse Events.

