6.3 ADVERSE EVENT ASSESSMENT

All study subjects will be evaluated for Adverse Events as defined in this protocol. All adverse events, regardless of severity, and whether or not they are ascribed to the study treatment, will be recorded in the source documents using standard medical terminology. Pre-existing conditions or diseases present at the 36-month exam that remain stable or change in a manner consistent with natural disease progression are not considered Adverse Events.

All Adverse Events will be evaluated beginning at the time of onset, and evaluation will continue until resolution or until the investigator determines that the subject's condition is stable. The investigator will take appropriate and necessary therapeutic measures required for resolution of the Adverse Event. Any medication necessary for the treatment of an Adverse Event must be recorded on the concomitant medication source document.

All AEs will be characterized by the following criteria:

- Event term,
- Intensity or severity,
- Expectedness,
- · Relationship to study treatment,
- Outcome, and
- Treatment or action taken.

Whenever possible, recognized medical terms should be used when recording AEs. Colloquialisms and/or abbreviations should not be used. Only one medical concept, preferably a diagnosis instead of individual symptoms, should be recorded as the event.

If known at the time of reporting, a diagnosis (i.e., disease or syndrome) should be recorded on the source document rather than individual signs and symptoms (e.g., record congestive heart failure rather than dyspnea, rales, and cyanosis). If a constellation of signs and/or symptoms cannot be characterized with a single medical diagnosis or syndrome, and they are considered unrelated to an encountered syndrome or disease at the time of reporting, these individual events should be recorded as separate AEs (e.g., if congestive heart failure and severe headache are observed at the same time, each event should each be recorded as an individual AE). If a diagnosis was not initially reported and is subsequently established, it should be reported as follow-up information and the original AE documents updated accordingly.

Adverse Events occurring secondary to other events (e.g., sequelae) should be identified by the primary cause. A "primary" event, if clearly identifiable, should represent the most accurate clinical term to record as the AE event term. For example:

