6.5 CLASSIFICATION OF ADVERSE EVENTS BY EXPECTEDNESS/RELATEDNESS

All AEs will be evaluated as to whether they are expected or unexpected. The sponsor will monitor and evaluate all study AEs to confirm the appropriate assignment of classification based on the collective nature, severity, and degree of incidence.

Expected (anticipated): An Adverse Event is expected when the nature, severity, or degree of incidence was previously described.

Unexpected (unanticipated): An Adverse Event is unexpected when the nature, severity, or degree of incidence was not previously described.

All AEs will be evaluated as to whether they are related to the device, as defined below:

Not Related: Strong evidence exists that the Adverse Event has a cause other than the investigational device (e.g. pre-existing condition or underlying disease, concurrent illness, or concomitant medication).

Possibly Related: There is a temporal association with the investigational device and it cannot be excluded as a cause, but other etiologies could possibly be the cause based upon available information.

Probably Related: There is a temporal association with the investigational device which makes a causal relationship probable where other etiologies are possible but unlikely to be the cause, based upon available information.

Definitely Related: Strong evidence exists that the investigational device definitely caused the Adverse Event. There is a temporal relationship between the event onset and the investigational device and the subject's clinical state and concomitant therapies have been ruled out as a cause, based upon available information.

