6.8 POSSIBLE ADVERSE EVENTS

Possible Adverse Events that might reasonably be expected to occur in this study are listed below. The time periods refer to the exam visit that occurs corresponding to the post-operative follow-up visit schedule (i.e., 36 months means the 36-month postoperative visit).

These specific examples of possible Adverse Events for VIS-2014-5YR include, but are not limited to:

Lids and Lashes

- Ptosis
- Hordeolum
- Chalazion
- Onset of or worsening to severe clinically significant lid margin disease (e.g., blepharoconjunctivitis, blepharitis, meibomitis, meibomian gland dysfunction, etc.)

Cornea

- Corneal dellen
- Corneal abrasion > 2mm
- Dry eye signs (moderate or severe) of corneal and/or conjunctival staining, etc., requiring prescription medication
- Corneal edema (moderate or severe)
- Corneal infiltrate or ulcer

Conjunctiva/Sclera

- Conjunctival cyst
- Conjunctival erosion
- Moderate or severe conjunctival injection
- Subconjunctival hemorrhage (not associated with an explant or concomitant procedure)
- Conjunctivitis (allergic, bacterial, viral)
- Scleral erosion
- Scleritis

Anterior Segment, Iris, Lens

- Persistent pupil abnormalities
- Posterior Synechiae
- Rubeosis Irides
- Anterior segment ischemia (Grades 2 4)
 - Grade 2: Decreased pupil reactivity (%CH < 25%)
 - Grade 3: Decreased pupil reactivity plus anterior chamber reaction (Grade 2 with cell and/or flare)
 - Grade 4: Corneal edema, anterior chamber reaction and decreased pupillary reactivity (Grade 3 with striate keratopathy)
- Anterior chamber cells or flare
- Intraocular Inflammation other than anterior chamber cells and flare (e.g. Vitritis)
- Two grade change in lens opacity as compared to preoperative baseline

Implants

Displaced, extruded, or missing implant segments

Intraocular Pressure

- Glaucoma
- Hypotony (IOP < 6 mm Hg)
- Increase in IOP of > 10 mm Hg over baseline or IOP > 30 mm Hg at two consecutive visits

BCDVA Loss

Decrease in BCDVA of greater than or equal to 2 lines (≥ 10 letters ETDRS)

Fundus

- Choroidal effusion
- Retinal detachment
- Retinal or vitreous hemorrhage
- Retinal hole
- Posterior vitreous detachment

Secondary Surgical Intervention

- Implant segment removal
- Exposed implant segments or conjunctival retraction requiring conjunctival reapproximation
- Cataract extraction
- Any other secondary surgical intervention

Other

- Eye pain requiring oral prescription pain medication

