APPENDIX 2: ANTERIOR SEGMENT ISCHEMIA (ASI): DETECTION, MITIGATION AND REPORTING

Anterior Segment Ischemia (ASI) is a potentially serious but most often self-limited response to decreased perfusion that even in severe cases generally resolves without sequelae or detrimental effects on vision. The rich collateral blood supply of the anterior segment likely explains its relatively benign common clinical course.

Decreased constriction of the pupil in response to light is the earliest physiological indicator of ASI and serves as a bellwether indicating diminished perfusion. Recovery of perfusion, when it occurs at this mild stage, avoids potential sequelae such as persistent pupillary abnormalities. Monitoring the pupillary reflex in the immediate postoperative period helps prevent progression by allowing prompt intervention to restore perfusion while the condition remains completely reversible.

In this clinical study of the VisAbility Micro Insert, Refocus has adopted digital infrared dynamic pupillometry as a sensitive indicator of neuromuscular disturbance secondary to decreased iris vascular perfusion in the immediate postoperative period. Pupillometry serves the primary purpose of evaluating the impact of surgery on perfusion and allowing for prompt removal of scleral implants from eyes that demonstrate compromised perfusion, thus reversing impaired pupillary function and preventing progressive damage from ischemia.

Clinical Syndrome, Natural History and Severity Grading

ASI represents an acute, generally self-limited response of the anterior segment of the eye to decreased vascular perfusion. While mild cases most often resolve without sequelae, more severe cases may develop persistent pupillary abnormalities and iris atrophy. Though rare, cataract and hypotony have been reported in a few isolated, very severe cases.

The clinical syndrome of ASI was first described in 1954 and has become recognized as an uncommon complication of surgery involving the extraocular muscles.¹ Risk factors for the development of ASI include advanced age, previous extraocular surgery, blood dyscrasias, hypercoagulable states, atherosclerosis, carotid artery disease and thyroid related immune orbitopathy. In the setting of strabismus surgery, these risk factors play a larger role in determining susceptibility to ASI than the number or combination of muscles operated.²

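### The undefined natural-progression exclusion in sections 6.0 and 6.3 conflicts with section 6.8, so whether worsening of a pre-existing condition counts as an adverse event can depend on the site

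*Combined protocol and SAP*

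**What the plan says.** Section 6.0 opens with a definition that ignores cause: "An Adverse Event (AE) is any untoward sign, symptom or disease observed during the study regardless of the suspected cause". It then sets aside pre-existing or chronic conditions that are stable, and goes further: "Changes in pre-existing or chronic conditions or diseases that are consistent with natural disease progression are not Adverse Events".

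Section 6.3 has the same two-sided structure. On recording it says: "All adverse events, regardless of severity, and whether or not they are ascribed to the study treatment, will be recorded in the source documents". It then declares the following not to be adverse events: "Pre-existing conditions or diseases present at the 36-month exam that remain stable or change in a manner consistent with natural disease progression".

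Section 6.5 has a separate relatedness scale. Its lowest category, Not Related, already covers underlying disease: "Strong evidence exists that the Adverse Event has a cause other than the investigational device (e.g. pre-existing condition or underlying disease".

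Section 6.8 lists possible adverse events by eye structure. Several items are thresholds for worsening and carry no natural-history exception. One is "Two grade change in lens opacity as compared to preoperative baseline". Others are lid margin disease that begins or worsens to severe, a BCDVA loss of at least 2 lines (10 ETDRS letters), and a two-grade worsening of other findings.

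Section 1.6 makes the SAE rate a primary safety outcome and the AE rate a secondary one. BCDVA, IOP rise, slit lamp findings and fundus findings are separate secondary safety outcomes.

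**The concern.** To call a worsening natural progression is, in effect, to say what caused it. In a study without a control group, the sound order is to count events by objective criteria and attribute them afterwards. Here the attribution comes first for one class of event, and whatever it removes never reaches the relatedness scale.

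The rule has no threshold, comparator or adjudication, so its application can vary between sites. The AE rate would then partly reflect local habit. The SAE rate could be affected too, because a finding must be an AE before it can be classed as an SAE. The sponsor's review of the collective nature, severity and incidence of AEs (sections 6.2 and 6.5) would also run on a list from which these events are already missing.

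**Working it through.** The plan states no sample size, expected AE rate or precision target, so there is no figure to reproduce. The check is mainly a comparison of sections.

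**1. Which outcomes the clause reaches.** Section 6.1 classifies an adverse event as serious if it meets a listed criterion, so SAEs are a subset of AEs. A change excluded under 6.0 or 6.3 leaves both counts.

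**2. Order of judgement.**

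| Section | Role of cause |
|---|---|
| 6.0, definition | None |
| 6.0 and 6.3, exclusion | Decides whether a change in a pre-existing condition is an AE at all |
| 6.3, recording rule | None, but it applies only to what already counts as an AE |
| 6.5 | Graded after recording; Not Related covers underlying disease |
| 6.8 | None in the listed worsening criteria |

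The exclusion therefore takes over work that 6.5 was written to do, and does so where nothing is kept in the AE record.

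**3. Which rule prevails.** Section 6.8 is introduced as a non-exhaustive set of examples. Nothing says that it overrides 6.0 and 6.3, or the reverse.

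**4. A worked case.** Take an eye graded N1 for nuclear opacity preoperatively and at month 36, and N3 at month 60, on the lens scale in Appendix 1. The change from preoperative baseline is 3 − 1 = 2 grades, so the 6.8 criterion is met. The opacity was present at the 36-month exam, so under 6.3 it is not an AE if the change is judged natural progression. One site records an AE and another does not, and each can cite the protocol.

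**5. What the clause does not reach.**
- New-onset conditions remain AEs whatever their cause.
- Explantation, anterior segment ischemia and segment exposure are primary outcomes listed in their own right.
- Slit lamp examination and BCDVA are scheduled at months 36, 48 and 60 (Table 1) and summarised whether or not an AE was recorded (sections 1.6, 5.2 and 5.3).

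**6. Whether the loss could be seen.** Section 5.2 describes the study as non-comparative. A footnote to Table 1 shows that controls in the parent trial's randomised sub-study were examined through 6 months only. No concurrent group covers months 36 to 60.

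**7. Size.** Let p be the true cumulative rate of events meeting a 6.8 criterion, s the share of them that are worsening of a pre-existing condition, and f the share of those judged natural progression. Then

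recorded rate = p × (1 − s × f), and relative loss = s × f.

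The documents give none of the three. With an assumed p of 10%:

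| s | f = 0.5 | f = 1 |
|---|---|---|
| 0.25 | 10% × (1 − 0.125) = 8.75% | 10% × (1 − 0.25) = 7.5% |
| 0.5 | 10% × (1 − 0.25) = 7.5% | 10% × (1 − 0.5) = 5.0% |
| 1.0 | 10% × (1 − 0.5) = 5.0% | 10% × (1 − 1) = 0% |

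The relative loss can lie anywhere from 0% to 100%. The table shows how the loss depends on s and f; it is not an estimate for this study.

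**The case against.** The strongest reply is that little is lost. The clause covers only pre-existing or chronic conditions. Lens grades, BCDVA, IOP, slit lamp and fundus findings are collected and summarised anyway, so a two-grade lens change or a 10-letter loss can be derived from the examination data whatever the site called it. Section 6.8 can also be read as the specific rule that displaces the general one, since its thresholds for worsening make sense only if progression from an earlier state can count. Section 6.2 separately requires notice of serious adverse effects within 24 hours. No example of a serious worsening that would be filtered out appears in the documents.

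Most of this stands, and it rules out stronger readings. A reader might infer that the clause removes age-related eye events in general, or that such events leave no trace in the data. The documents support neither: a new cataract or new glaucoma is still an AE, and the examination findings remain available for comparison with outside rates. A reader might also infer that the investigator is the appointed judge. Neither clause names one; that the site decides is a reasonable inference only. Nor does Appendix 2 show that lens change at months 36 to 60 is likely to come from the device. It says "Though rare, cataract and hypotony have been reported in a few isolated, very severe cases", and it describes ischemia as an acute response.

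Two parts of the reply do not dispose of the point. Reading 6.8 as the controlling rule is possible, but the protocol does not say so. And the planned examination summaries carry no assessment of seriousness, relatedness or outcome, so they cannot repair the AE and SAE rates, which are outcomes in their own right. The notice duty in 6.2 sits within the provisions on unanticipated device effects and does not say that such an event enters the AE rate.

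**Conclusion.** The concern holds in a limited form. Sections 6.0 and 6.3 let an undefined, cause-like judgement exclude worsening of a pre-existing or chronic condition before it is recorded, against the opening definition in 6.0 and the criteria in 6.8. The result can be a site-dependent undercount in the secondary AE rate and, where a worsening is serious, in the primary SAE rate.

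The direction is clear, since an exclusion can only lower the count. The size cannot be computed from the documents. The conclusion assumes that at least some sites would follow 6.0 and 6.3 as written when a 6.8 criterion is met. It would be wrong to conclude that the study loses its information on age-related eye findings, or that the SAE rate is shown to be materially biased. The plan should be changed, but the defect is moderate, because much of the underlying data stays in the examination record.

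**What to change.** Add to sections 6.0 and 6.3 that any finding or worsening that meets a 6.8 criterion is recorded as an AE irrespective of natural progression, and that the view that it reflects natural progression is entered under relatedness in 6.5. Limit the natural-progression exclusion to changes that meet no 6.8 criterion. This also settles which section prevails.

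The cost is protocol wording and some additional AE entries, drawn from examinations already scheduled. The downside is a somewhat higher crude AE rate. Showing the AE table by relatedness category lets a reader see how much of it was attributed to underlying disease.

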6.1 SERIOUS ADVERSE EVENTS (SAE)

An Adverse Event should be classified as a Serious Adverse Event (SAE) and reported as such, if it meets one or more of the following criteria:

- It results in death (i.e., the Adverse Event causes or leads to death).
- It is life threatening (i.e., the Adverse Event places the subject at immediate risk of death).
- It is considered sight-threatening and requires intervention to prevent permanent impairment or damage.
- It requires or prolongs inpatient hospitalization. Hospitalization or prolonged hospitalization for diagnostic or elective surgical procedures for preexisting conditions are not SAEs.
- It results in persistent or significant disability/incapacity (i.e., the Adverse Event results in substantial disruption of the subject's ability to conduct normal life functions) or impairment of a body function or damage to body structures.
- It results in a congenital anomaly/birth defect in a neonate/infant born to a mother exposed to the investigational product.
- It does not meet any of the above serious criteria but may jeopardize the subject or may require medical or surgical intervention to prevent one of the outcomes listed above.

If a subject is hospitalized to undergo a medical or surgical procedure as a result of an Adverse Event, the event responsible for the procedure, not the procedure itself, should be recorded as the event. (For example, if a subject is hospitalized to undergo coronary bypass surgery, record the heart condition that necessitated the bypass).

Investigators must notify Refocus of any SAE within 24 hours of observing or learning of the event. For initial SAE reports, Investigators should record all case details that can be gathered within 48 hours on the SAE Form and fax immediately upon completion to Refocus.

6.2 UNANTICIPATED ADVERSE DEVICE EFFECTS (UADE)

An unanticipated adverse device effect (UADE) is any serious adverse effect on health or safety or any life-threatening or sight-threatening problem or death caused by or associated with a device, if that effect, problem, or death was not previously identified in nature, severity or degree of incidence. UADEs also include any unanticipated sight-threatening events and any other unanticipated serious problem associated with a device that relates to the rights, safety, or welfare of subjects.

Investigators must notify Refocus of any serious adverse effect on health or safety within 24 hours of observing or learning of the event. The sponsor will monitor and evaluate all study AEs to ensure the collective nature, severity, and degree of incidence is measured. Refocus will be responsible for informing the appropriate Regulatory Authorities, IRBs, and Investigators participating in the study of the UADE.

6.3 ADVERSE EVENT ASSESSMENT

All study subjects will be evaluated for Adverse Events as defined in this protocol. All adverse events, regardless of severity, and whether or not they are ascribed to the study treatment, will be recorded in the source documents using standard medical terminology. Pre-existing conditions or diseases present at the 36-month exam that remain stable or change in a manner consistent with natural disease progression are not considered Adverse Events.

All Adverse Events will be evaluated beginning at the time of onset, and evaluation will continue until resolution or until the investigator determines that the subject's condition is stable. The investigator will take appropriate and necessary therapeutic measures required for resolution of the Adverse Event. Any medication necessary for the treatment of an Adverse Event must be recorded on the concomitant medication source document.

All AEs will be characterized by the following criteria:

- Event term,
- Intensity or severity,
- Expectedness,
- · Relationship to study treatment,
- Outcome, and
- Treatment or action taken.

Whenever possible, recognized medical terms should be used when recording AEs. Colloquialisms and/or abbreviations should not be used. Only one medical concept, preferably a diagnosis instead of individual symptoms, should be recorded as the event.

If known at the time of reporting, a diagnosis (i.e., disease or syndrome) should be recorded on the source document rather than individual signs and symptoms (e.g., record congestive heart failure rather than dyspnea, rales, and cyanosis). If a constellation of signs and/or symptoms cannot be characterized with a single medical diagnosis or syndrome, and they are considered unrelated to an encountered syndrome or disease at the time of reporting, these individual events should be recorded as separate AEs (e.g., if congestive heart failure and severe headache are observed at the same time, each event should each be recorded as an individual AE). If a diagnosis was not initially reported and is subsequently established, it should be reported as follow-up information and the original AE documents updated accordingly.

Adverse Events occurring secondary to other events (e.g., sequelae) should be identified by the primary cause. A "primary" event, if clearly identifiable, should represent the most accurate clinical term to record as the AE event term. For example:

Orthostatic hypotension \Rightarrow fainting and fall to floor \Rightarrow head trauma \Rightarrow neck pain

The primary event is orthostatic hypotension and the sequelae are head trauma and neck pain.

